### **9.6 Statistical Methods**

This section describes the statistical methods that address the primary and secondary objectives as well as a key exploratory objective for viral RNA endpoints. Methods related to other exploratory objectives will be described in the sSAP. Methods related to PK analysis and PK/PD modeling will be described in a separate modeling and simulation plan authored by QP2. Methods related to dose response analysis using MCP-MOD will be described in a separate dose response analyses plan. Methods related to analyses of biomarkers and other exploratory samples will be described separately.

Efficacy results that will be deemed to be statistically significant after consideration of the type I error control for interim analyses are discussed in Sections 9.7 and 9.8. There are no additional adjustments for multiplicity. Statistical testing and inference for safety analyses are described in Section 9.6.2.

### 9.6.1 Statistical Methods for Efficacy Analyses

The stratified log-rank test will be used for the comparison of MK-4482 with placebo for the primary endpoint of the time-to-sustained recovery. Stratification factors are specified in Section 6.3.2. The relevant treatment efficacy parameter is the “sustained recovery rate ratio” (for MK-4482 relative to placebo), which is akin to the hazard ratio in survival analysis but for the beneficial outcome of sustained recovery. Sustained recovery rate ratios will be based on the stratified Cox Proportional Hazards regression model with stratification by factors specified in Section 6.3.2. Geographic region will not be used as a covariate in the primary analyses, but it may be considered as an additional stratification factor for the stratified log rank test and as a covariate for the Cox Proportional Hazards regression model for sensitivity analysis if it does not cause sparse data issues. The number of regions along with the specific countries contained within each region will be described in the sSAP. The Efron approximation will be used for handling ties. Failure to recover will be censored at Day 29. Death before Day 29, including death following a prior recovery, will be censored at Day 29 to eliminate any bias that would be introduced by censoring at time of death. Lost to follow-up before Day 29, regardless of prior recovery, will not be considered a sustained recovery and will be censored at the day of last contact. Withdrawal (ie, discontinuation from the study for reasons other than death or lost to follow up) before Day 29, regardless of prior recovery, will not be considered a sustained recovery and will be censored at the day of discontinuation.

Participants who initiate Sponsor-designed standard of care for treatment for COVID-19 48 hours or more following start of randomized study therapy will be treated as a failure to recover. Sustained recovery rate ratios greater than 1 indicate a benefit for MK-4482. Superiority will be concluded based on p-value boundaries as described in Sections 9.7 and 9.8.

A sensitivity analyses for the primary efficacy endpoint will be performed in the MITT population that does not impute “failure to recover” for participants who initiate Sponsor-designed standard of care for treatment for COVID-19 following start of randomized study therapy. In the case where the number of participants who require re-hospitalization but are then discharged again (or medically ready for discharge) before Day 29 exceeds 5% of the total MITT population, an additional sensitivity analysis will be performed in which all participants with re-hospitalizations by Day 29 are considered as not meeting the primary endpoint.

If superiority of MK-4482 over placebo is demonstrated as assessed by time-to-sustained recovery at the end of Part 2, the superiority of MK-4482 over placebo as assessed for the key secondary endpoint of all-cause mortality at Day 29 will be tested. Due to the relatively low number of deaths expected and the large number of strata levels, the unstratified Miettinen and Nurminen method [Miettinen, O. 1985] will be used to estimate and test the treatment difference for all-cause mortality. Every effort will be made to ascertain survival status for all participants. Missing data for this endpoint will be treated as failure (M=F approach) in the MITT population.

Ordinal outcome scales such as Pulmonary and Pulmonary+ will be analyzed using the cumulative logits function and the proportional odds model as described by McCullagh [McCullagh, P. 1980]. This methodology provides an estimate of the common odds ratio for assessing differences between treatment groups. In addition to a term for treatment group, the model will include terms for the stratification factors specified in Section 6.3.2. In addition, the proportion of participants in each ordinal scale category by treatment groups will also be presented.

The National Early Warning Score and the WHO 11-point ordinal scale score will be categorized to ordinal outcomes and will be further analyzed using the same approach as for Pulmonary and Pulmonary+ outcomes.

The viral RNA endpoints at earlier time points (Day 3 and EOT) will be important for the dose selection decision from Part 1 of the study. Change from baseline in SARS-CoV-2 RNA titer, calculated as  $\log_{10}$  (post) minus  $\log_{10}$  (baseline), as measured by quantitative RT-PCR of samples from NP and OP swabs will be summarized separately by treatment group and time point. The DAO approach will be used to handle missing data for these summary statistics. In addition to summary statistics, treatment differences in change in SARS-CoV-2 RNA titer from baseline over time will be estimated using longitudinal models. Graphical presentations of the change from baseline will be presented and the impact of baseline viral RNA level will be explored using subgroup analyses (defined by level of baseline viral RNA) and analyses/summaries that exclude participants with low baseline levels (eg, viral RNA  $<10^6$  copies/mL).

Percentage of participants with undetectable viral RNA (below limit of detection) as measured by qualitative RT-PCR of samples from NP and OP swabs will be summarized separately by treatment group and time point. Between-treatment differences and 95% confidence intervals will be estimated using the stratified Miettinen and Nurminen method [Miettinen, O. 1985].

A detailed analysis strategy for key efficacy endpoints is listed in [Table 5](#). The strategy to address multiplicity issues with regard to multiple efficacy endpoints and interim analyses is described in Section 9.7, Interim Analyses and in Section 9.8, Multiplicity.

Table 5 Analysis Strategy for Key Efficacy Endpoints

Endpoint/Variable (Description, Time Point)	Primary vs. Supportive Approach a	Statistical Method b	Analysis Population	Missing Data and Data Imputation Approach
Primary Endpoint				
Time-to-sustained recovery from randomization through Day 29	P (MITT) S (PP)	Stratified log-rank test c  Stratified Cox Proportional Hazards regression d	MITT PP	
Missing data will not be imputed.
 
Participants who initiate Sponsor-designated standard of care for treatment for COVID-19 48 hours or more following start of randomized study therapy will be treated as a failure to recover.
 
A sensitivity analysis for the primary efficacy endpoint will be performed in the MITT population that does not impute “failure to recover” for participants who initiate Sponsor-designated standard of care for treatment for COVID-19.
 
Depending upon the number of participants who required re-hospitalization but were discharged or medically ready for discharge again before Day 29, an additional sensitivity analyses will be performed in which all participants with re-hospitalizations by Day 29 are considered as not meeting the primary endpoint.
 
Failure to recover will be censored at Day 29. Death will also be censored at Day 29. Recovery followed by subsequent lost to follow up before Day 29 will be censored at the day of lost to follow up. Withdrawal (ie, discontinuation from the study for reasons other than death or lost to follow up) before Day 29 will be censored at the day of discontinuation.

Endpoint/Variable (Description, Time Point)	Primary vs. Supportive Approach a	Statistical Method b	Analysis Population	Missing Data and Data Imputation Approach
Secondary Endpoints				
All-cause mortality through Day 29	P (MITT) S (PP)	Unstratified M & N method c	MITT PP	Missing = Failure (M=F) – MITT Data as Observed (DAO) - PP
Odds of a more favorable response on Pulmonary score at Day 3, EOT, Day 10, Day 15, and Day 29	P (MITT) S (PP)	Proportional odds model d	MITT PP	Model-based
Odds of a more favorable response on Pulmonary+ score at Day 3, EOT, Day 10, Day 15, and Day 29	P (MITT) S (PP)	Proportional odds model d	MITT PP	Model-based
Odds of a more favorable response in the clinical risk of mortality category from the National Early Warning Score at EOT	P (MITT) S (PP)	Proportional odds model d	MITT PP	Model-based
Odds of a more favorable response on the WHO 11-point ordinal scale on Day 3, EOT, Day 10, Day 15 and Day 29	P (MITT) S (PP)	Proportional odds model d	MITT PP	Model-based
EOT=End of Treatment; MITT= modified intent-to-treat; M & N= Miettinen and Nurminen; PP=Per-protocol; WHO=World Health Organization.				

a P=Primary approach; S=Supportive approach.

b Statistical models are described in further detail below:

c The stratified log-rank test includes stratification factors specified in Section 6.3.2.

d Stratified Cox Proportional Hazards regression includes terms for treatment, stratification factors specified in Section 6.3.2.

e Unstratified Miettinen and Nurminen method.

f Proportional odds model includes terms for treatment and stratification factors specified in Section 6.3.2.

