### 1.3 Schedule of Activities

Study Period:	Screening	Intervention					Follow-Up				Notes
Visit Number/Title:	1	2	3	4	5	6	7	8	9	10	
Scheduled Day (and Window):	Screening ( $\leq$ 24 hours before rand.) a	Day 1 b	Day 2	Day 3	Day 4	EOT	Day 10 ( $\pm 1$ day)	Day 15 ( $+3$ days)	Day 29 ( $+3$ days)	LFU Month 7 ( $\pm 1$ Month) c	
Type of Visit H = Hospitalized C = Clinic or At-home visit V= Virtual Visit	H	H	H/C/ V	H/C	H/C/ V	H/C	H/C	H/C	H/C	V	Virtual, Clinic, and At-home visits are only allowed after discharge. Virtual visits (Day 2 and Day 4) will consist of Concomitant Medication and AE/SAE collection only. When a virtual visit is listed, a clinic or home visit is not required. Virtual visits may be conducted at the investigator's discretion.
Administrative Procedures											
Informed Consent	X										
Informed Consent for PBMC Collection (Optional)	X										Only a subset of participants at selected sites
Register Study Visit in IRT	X	X									
Inclusion/Exclusion Criteria	X d	X e									Including review of SARS-CoV-2 (+) local test results.
Participant Identification Card	X	X									Randomization number must be added to card at randomization.
Medical History	X										Including day of onset of COVID-19 signs/symptoms
Prior/Concomitant Medication Review	X	X	X	X	X	X	X	X	X		Including COVID-19 standard of care therapies and supportive care

Study Period:	Screening	Intervention					Follow-Up				Notes
		1	2	3	4	5	6	7	8	9	
Scheduled Day (and Window):	Visit Number/Title: Screening ( $\leq 24$ hours before rand.) a	Day 1 b	Day 2	Day 3	Day 4	EOT	Day 10 ( $\pm 1$ day)	Day 15 (+3 days)	Day 29 (+3 days)	LFU Month 7 ( $\pm 1$ Month) c	
Intervention Randomization		X b									COVID-19 severity categorization entered in IRT at randomization must be based on values obtained on Day 1 prior to randomization
Collect/Update Secondary Contacts for Participant	X					X		X	X		Also to occur upon discharge
MK-4482 or Placebo Administration f		X	X	X	X	X					First dose is preferably administered on Day 1 (randomization), but must be within 24 hours of randomization.
MK-4482 or Placebo - Observed Dosing						X					The morning dose at EOT will be observed to facilitate PK blood collection.
Efficacy Procedures											

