#### **6.3.2 Stratification**

Intervention randomization will be stratified according to the following factors:

1. Time from symptom onset prior to the day of randomization ( $\leq 5$  days,  $>5$  days)
2. Age ( $\leq 60$  years,  $>60$  years)
3. Remdesivir use for treatment of the index diagnosis of COVID-19 prior to or at the time of randomization (yes, no)

Based on the viral kinetics of SARS-CoV-2 and the mechanism of action of MK-4482, treatment with antiviral therapy is likely to have a greater benefit with early treatment ( $\leq 5$  days) rather than late treatment ( $>5$  days). Older age is also associated with more severe outcomes, and the WHO notes that people older than 60 years are at higher risk for severe illness due to COVID-19. Finally, remdesivir has been demonstrated to shorten the time to recovery in hospitalized patients with COVID-19 and may be used concurrently in this study. The selection of these criteria as stratification factors will help ensure that the treatment groups will be well balanced within each stratum and the study results will not be confounded by factors suspected to have a potential impact on a participant's response to study intervention.

Of note, enrollment of participants with severe COVID-19 (Appendix 9) will be limited to 50% of the total planned sample size in both Parts 1 and 2.

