### **8.1.2 Inclusion/Exclusion Criteria**

All inclusion and exclusion criteria will be reviewed by the investigator, who is a qualified physician, to ensure that the participant qualifies for the study.

The SARS-CoV-2 test result must be reviewed for participant eligibility and data entered into the eCRF including date specimen collected, sample type (eg, NP swab, OP swab, mid-turbinate swab, saliva, etc.), test method (eg, RT-PCR) and result (positive result is required).

Assessments required for COVID-19 severity categorization (Appendix 9) for IRT (vital signs, COVID-19 signs/symptoms assessment, respiratory measures, oxygen therapy, ongoing medical history) must be completed and documented on Day 1 prior to calling IRT in order to randomize. All other Day 1 assessments must be completed on Day 1 prior to first dose of study intervention.

The following local laboratory results must be available for all participants from within 72 hours prior to randomization: serum creatinine, platelets, and absolute neutrophil count (segmented neutrophils and bands). In participants with reported history of HBV or HCV, ALT and AST must be available from within 72 hours prior to randomization to support determination of eligibility. In WOCBP, a negative local serum pregnancy test is required within 24 hours of the first dose of study drug per inclusion criteria.

All other inclusion/exclusion criteria determination (eg, HIV status, pancreatitis, etc.) can be based on participant-reported medical history, available medical records, and the most recently available laboratory results for the participant (eg, HIV RNA viral load or CD4 count).

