## 9.4.1 Efficacy/Pharmacokinetics Endpoints

### 9.4.1.1 Efficacy Endpoints

#### Primary:

- Time-to-sustained recovery from randomization through Day 29

Sustained recovery is defined as:

1. Participant is alive and not hospitalized through Day 29 (including those re-hospitalized and discharged again before Day 29). Includes those discharged to home, home with nursing care, a rehabilitation facility, a long-term care facility, or a non-hospital intermediate care facility.

OR

2. Participant is alive and medically ready for discharge through Day 29 as determined by the investigator. Includes those hospitalized or re-hospitalized participants who no longer require ongoing medical care but remain hospitalized for infection-control reasons or due to delay in identifying living accommodation outside the hospital.

The time to sustained recovery is the time from randomization to the day of discharge or the day that the participant is medically ready for discharge for participants who are not re-hospitalized. For participants who are re-hospitalized but discharged again before Day 29, the time to sustained recovery is the time from randomization to the day of the latest discharge.

The following events do not meet the definition of sustained recovery:

- Died
- Discharged to hospice care
- Remains in facility receiving ongoing medical care
- Transferred to a general hospital unit or another hospital for ongoing medical care
- Re-hospitalized and not discharged or not medically ready for discharge again before Day 29.
- Initially discharged to home, home with nursing care, a rehabilitation facility, a long-term care facility, or a non-hospital intermediate care facility, but subsequently transferred by Day 29 to hospice care or to a medical care facility due to worsening condition.
- Discharged but lost to follow-up through Day 29.

Section 9.6.1 describes the censoring dates for these participants.

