## 9.9 Sample Size and Power Calculations

### 9.9.1 Sample Size and Power Calculations for Efficacy Analyses (Part 2)

The primary analysis of Phase 3 study endpoints will include ~1000 participants from Part 2 of the study (~500 for the selected MK-4482 group and ~500 for the placebo group) who meet the criteria for inclusion in the MITT population. The primary endpoint is time-to-sustained recovery. The study has overall power of 90% to demonstrate that participants treated with MK-4482 have a higher rate of sustained recovery than participants treated with placebo at an overall one-sided, 2.5% alpha-level, if the underlying constant sustained recovery rate ratio between treatment groups is 1.3.

The power and sample size are based on the following assumptions: 1) the time-to-sustained recovery follows an exponential distribution with sustained recovery rates of 0.351 and 0.270 for the MK-4482 and placebo groups, respectively, 2) a futility/efficacy interim analysis at 50% information as outlined in Section 9.7, 3) an enrollment period of 10 weeks, and 4) dropout hazard rates of 0.02 for both the MK-4482 and placebo groups, respectively. The above sustained recovery rates correspond to approximately 366 (73%) and 319 (64%) sustained recovery events for the MK-4482 and placebo groups, respectively. These are nearly identical to the recovery rates presented for remdesivir and placebo in the NEJM [Beigel, J. H., et al 2020]. The calculation was computed using both EAST and gsDesign. To meet the statistical criterion for success (one-sided p value $\leq$ 0.019 at the final analysis), the observed sustained recovery rate ratio must be approximately 1.17 or larger.

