### Severe COVID-19:

Must have **ONE or MORE** of the following:

- Shortness of breath **at rest**
- Respiratory rate  $\geq 30$  breaths per minute
- Heart rate  $\geq 125$  beats per minute
- $\text{SpO}_2 \leq 93\%$  on room air or on supplemental oxygen for a reason other than COVID-19 which HAS NOT increased since onset of COVID-19 signs/symptoms
- On supplemental oxygen for a reason other than COVID-19 which HAS increased since onset of COVID-19 signs/symptoms, regardless of  $\text{SpO}_2$
- On  $> 2$  liters/min supplemental oxygen for COVID-19 (but was not previously on supplemental oxygen), regardless of  $\text{SpO}_2$
- $\text{PaO}_2/\text{FiO}_2 < 300$

AND

Must **NOT** have respiratory failure, shock, or multi-organ dysfunction/failure (see definitions in Critical COVID-19 below)

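### The primary analysis does not use the Day 1 severity category that IRT already holds; adding it as a two-level stratum is a cheap possible gain in power, not the repair of an error

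*Combined protocol and SAP*

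**What the plan says.** Section 9.6.1 gives a stratified log-rank test for time to sustained recovery and adds that "Sustained recovery rate ratios will be based on the stratified Cox Proportional Hazards regression model with stratification by factors specified in Section 6.3.2". Section 6.3.2 lists three binary factors (symptom onset up to or beyond 5 days, age up to or over 60, remdesivir yes or no), which makes 8 strata. The Table 5 footnotes repeat this.

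Severity is already collected. The Schedule of Activities (Section 1.3) states: "COVID-19 severity categorization entered in IRT at randomization must be based on values obtained on Day 1 prior to randomization". Section 8.1.2 and Appendix 9 say the same, and Section 6.3.2 relies on the category for a cap: "enrollment of participants with severe COVID-19 (Appendix 9) will be limited to 50% of the total planned sample size". In the planned efficacy analyses, severity appears only in the subgroup list of Section 9.10.

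Geographic region is the only extra factor considered for the primary endpoint, and only "for sensitivity analysis if it does not cause sparse data issues".

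The sample size in Section 9.9.1 assumes that "the time-to-sustained recovery follows an exponential distribution with sustained recovery rates of 0.351 and 0.270 for the MK-4482 and placebo groups", respectively, a ratio of 1.3.

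**The concern.** Section 9.4.1.1 defines recovery as being out of hospital or medically ready to leave: "Includes those hospitalized or re-hospitalized participants who no longer require ongoing medical care but remain hospitalized for infection-control reasons". Appendix 9 defines severity by oxygen need, SpO2, respiratory rate, heart rate and dyspnoea. One route into the severe category, for example, is "On supplemental oxygen for a reason other than COVID-19 which HAS increased since onset of COVID-19 signs/symptoms". These bear directly on readiness for discharge, so severity is a natural prognostic factor for this endpoint.

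When a strong prognostic factor is left out of a stratified log-rank test, the patients compared within each stratum are more mixed than they need be, and the rate ratio is pulled towards 1. The test keeps its type I error but can lose power. What is at stake is power for the primary hypothesis and the sharpness of the IA3 futility and efficacy decisions, from a baseline value held for everyone.

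**Working it through.** **1. The plan's own figures reproduce.** Inputs from Sections 9.7 to 9.9.1: 500 per arm, rates 0.351 and 0.270, dropout hazard 0.02, 28 days of follow-up. The time unit of the rates is not stated; taking it as weeks reproduces the event counts.

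Events = 500 × λ/(λ+0.02) × (1 − exp(−4(λ+0.02))):
- MK-4482: 500 × 0.351/0.371 × (1 − e^−1.484) = 365.8 (stated 366)
- Placebo: 500 × 0.270/0.290 × (1 − e^−1.16) = 319.6 (stated 319)

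Drift = ln(1.3) × √685/2 = 3.433. In a two-look design with gamma = −1 spending:
- The interim efficacy criterion is p = 0.0094, ratio 1.289; the final criterion is p = 0.0194, ratio 1.171.
- Overall power is 90.4% if the futility bound is followed and 91.9% if it is ignored (stated 90%).
- The final test alone at 0.019 gives 3.433 − 2.075 = 1.36, or 91.3%. This is the baseline for the comparisons below.

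**2. What severity would add.** The documents give no prognostic strength, so it is an assumption: severe patients recover at 1.0, 0.7, 0.5 or 0.4 times the rate of others.

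Simulation, 10,000 runs per scenario, both analyses on the same data (standard error of the power difference 0.12 to 0.29 points):
- 1000 participants, 1:1 in blocks of 2 within the 8 planned strata, 4 weeks of follow-up, dropout 0.02 per week.
- Baseline rate solved so that placebo recovery without dropout is 1 − exp(−4 × 0.27) = 66%.
- Assumed mix: onset over 5 days 55%; age over 60 45% (rate × 0.8); remdesivir 40%.
- Severe share: 50% (the cap), or 30% with severe disease correlated with age (odds ratio 2) and remdesivir (odds ratio 4).
- One treatment ratio across severity levels, set so that the planned 8-stratum Cox estimate is 1.30. With 50% severe, the within-severity ratios are then 1.300, 1.305, 1.322 and 1.340.
- Mean events 684 to 686.

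Final-test power (%), 8 strata versus 16 with severity added:

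| Severe vs other rate | 50% severe | 30% severe, correlated |
|---|---|---|
| 1.0 | 91.2 vs 90.9 | 91.5 vs 91.0 |
| 0.7 | 91.0 vs 91.5 | 91.3 vs 91.5 |
| 0.5 | 91.3 vs 93.8 | 91.5 vs 93.3 |
| 0.4 | 91.5 vs 95.5 | 91.4 vs 94.5 |

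A separate 4,000-run simulation gave 91.3 vs 90.8, 91.5 vs 91.5, 90.9 vs 93.3 and 91.2 vs 95.8, the same pattern within simulation error.

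**3. IA3** (500 participants, 50% severe, about 342 events, criteria of Section 9.7; crossing probabilities in %, 8 vs 16 strata):

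| Severe vs other rate | Early efficacy | Futility |
|---|---|---|
| 1.0 | 51.8 vs 50.1 | 4.0 vs 4.2 |
| 0.7 | 51.8 vs 51.8 | 3.9 vs 3.9 |
| 0.5 | 52.3 vs 56.1 | 3.6 vs 2.9 |
| 0.4 | 52.9 vs 61.0 | 3.7 vs 2.3 |

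**4. Type I error.** Null rejection at nominal 1.9% was 1.9 vs 1.7% (50% severe) and 1.6 vs 1.8% (30% severe, 10% on remdesivir). Both analyses are valid.

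**5. Stratum size.** 16 strata average 1000/16 = 62.5 participants, 685/16 = 43 events at the final analysis and 343/16 = 21 at IA3.

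**The case against.** The plan analyses by exactly the factors it randomises on and gives reasons for them, which is coherent. It is also deliberately sparing with strata: region is kept out of the primary analysis, and Section 9.6.1 leaves mortality unstratified partly because there are many strata. The treatment effect will in any case be shown within mild, moderate and severe disease. All of this is fair, but subgroup plots give the primary test no power, and a two-level split adds only one binary factor.

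The stronger objection is that the gain rests on something the documents do not give. Several features could weaken the gradient: critical disease is excluded, moderate disease can include up to 2 L/min of oxygen, and heart rate alone can place a patient in the severe category. Age and remdesivir may already carry part of the severity information. The simulations also assume one treatment ratio across severity levels. At a severe rate of 0.5 and 50% severe, ratios of 1.20 (non-severe) and 1.45 (severe) give 90.9 vs 90.6%, so the gain disappears; the opposite pattern, 1.45 and 1.15, gives 83.9 vs 93.6%. These limits stand, and they are why this remains an optional improvement.

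A reader might go further and infer that the trial is underpowered. If 1.3 were the ratio within severity levels, planned final-test power at 50% severe would be 89.9, 87.1 and 84.2% for severe rates of 0.7, 0.5 and 0.4. The documents do not support that reading: Section 9.9.1 gives one exponential rate per whole arm, so 1.3 is most naturally the severity-unadjusted ratio, and the planned power then stands.

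**Conclusion.** This is a cheap improvement, not an error. The planned test is valid, its power reproduces, and the omission does not bias the comparison under the null.

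Relative to about 91%, adding severity changes final-test power by about −0.3 to −0.5 points if severity is not prognostic, 0 to +0.5 at a severe rate of 0.7, +2 to +2.5 at 0.5 and +3 to +4 at 0.4. At IA3 the early-efficacy crossing changes by −1.7 points in the first case (51.8 to 50.1%) and +8.1 in the last (52.9 to 61.0%, at 50% severe).

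These figures rest on the assumed prognostic strength, a similar treatment ratio across severity levels, the assumed stratum mix, and continuous recovery times. The simulation does not model deaths censored at Day 29 or the rule that counts late-started standard of care as failure. The exchange is favourable if severity is strongly prognostic and close to neutral at 0.7 or weaker.

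**What to change.** By protocol amendment before any Part 2 unblinding (the opening of Section 9 requires one for a change to the primary method):

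- Add IRT Day 1 severity, severe versus mild/moderate, as a further stratum in the primary log-rank test and Cox model in Section 9.6.1 and Table 5.
- Prespecify a treatment-blind rule for pooling sparse strata at IA3 and at the final analysis.
- Describe the rate ratio as conditional on severity, including where the IA3 criteria of 1.071 and 1.289 are applied.

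Part 1 can inform the decision, because Part 2 starts only after Part 1 is analysed (Section 9.2) and Part 1 is kept out of the Part 2 efficacy analysis (Section 9.5.1). At the planned recovery proportion, 300 × 685/1000 gives about 205 events. With an even severity split the standard error of the log severity ratio is about 2/√205 = 0.14, enough to tell a ratio of 0.5 from 1.0.

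Costs: an amendment, no new data, 16 strata instead of 8, and a within-severity estimand. If severity is not prognostic, up to about 0.5 power points are lost at the final analysis and about 1.7 points of early-efficacy crossing at IA3. In a sparse case (30% severe, 10% on remdesivir) the smallest cell averaged 5.5 participants, and power was 90.8 vs 90.4% at a severe rate of 1.0 and 91.3 vs 93.0% at 0.5.

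A lighter option is a prespecified severity-stratified sensitivity analysis, as the plan allows for region. It leaves the primary test and its ratio unchanged, but also gives the primary test none of the gain.
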